5.2. Treatment Groups

This is an open-label, single-arm study. Participants will be summarized overall by total only.

5.3. Analysis Populations

5.3.1. Full Analysis Set

The FAS includes all participants enrolled in the study who received at least 1 dose of study drug.

The FAS will be used for the summary of demographics, baseline characteristics, participant disposition, and analyses of all efficacy and safety data.

5.3.2. [REDACTED]

6. BASELINE, EXPOSURE, AND DISPOSITION VARIABLES AND ANALYSES

[Appendix A](#) provides a list of planned tables and listings. Sample data displays are included in a separate document.

6.1. Baseline and Demographics, Physical Characteristics, and Disease History

6.1.1. Demographics

The following demographics will be summarized for the FAS: age, sex, race, ethnicity, weight, height, and BMI.

6.1.2. Baseline Disease Characteristics

The following baseline disease characteristics will be summarized for the FAS:

- Years since first onset of SS
- Severity of disease (Mild/Moderate/Severe)
- Current state of disease (Progressive/Stable)
- Prior or current treatment for SS (No/Yes)
- Prior surgery (No/Yes)
- Type of disease (Glandular/Extraglandular [categories of symptoms])
- Other autoimmune disease (No/Yes)
- Oral dryness (No/Yes [years since oral dryness started])
- Ocular dryness (No/Yes [years since ocular dryness started])

6.1.3. Prior Therapy

Prior medication information for SS will be used to identify medication received by participants before enrollment into the study. Prior medications for SS will be summarized.

6.1.4. General Medical History

For participants in the FAS, general medical history will be summarized. This summation will include the number and percentage of participants with significant medical history for each body system/organ class as documented on the CRF.

6.2. Disposition of Participants

The number and percentage of participants who were treated, completed study treatment, completed the study, discontinued study treatment with a primary reason for discontinuation, and discontinued from the study with a primary reason for withdrawal will be summarized for the FAS. The number of participants enrolled by site will also be provided.

6.3. Protocol Deviations

Protocol deviations recorded on the CRF will be presented in the participant data listings. A summary table of major protocol deviations will also be provided.

6.4. Exposure

For participants in the FAS, descriptive statistics will be provided for duration of treatment, average daily dose, and total dose. Duration of treatment with INCB050465 is defined as the number of days from Day 1 to the date of last record of INCB050465 administration.

6.5. Study Drug Compliance

For participants in the FAS, overall compliance (%) for INCB050465 will be calculated for all participants as

$$\text{Compliance (\%)} = 100 \times [\text{total number of tablets dispensed} - \text{total number of tablets returned}] / [\text{total intended number of tablets}].$$

The total intended number of tablets will be based on the earliest study day of permanent discontinuation of the study drug. The total intended number of tablets is defined as the sum of the tablets prescribed by the investigator accounting both for planned dose modifications as well as those modifications mandated by the investigator.

6.6. Prior and Concomitant Medication

For participants in the FAS, prior medications and concomitant medications will be coded using the WHO Drug Dictionary and summarized by WHO drug class and WHO drug term. Results will be summarized as number and percentage of participants with prior and concomitant medications by PT and WHO drug class.

[figure not shown]
7. EFFICACY

[Appendix A](#) provides a list of planned tables and listings. Sample data displays are included in a separate document. All efficacy analyses are exploratory. Hence, no p-values will be provided, and multiple adjustment will not be made.

7.1. Efficacy Parameters

7.1.1. Ultrasound of Salivary Glands

The echostructure of each gland on B-mode images will be graded on a 5-point scales (0 to 4) as described by Gazeau et al (2018). Grade 0 indicates a normal homogeneous gland, Grade 1 small hypoechoic areas with hyperechoic bands, Grade 2 multiple hypoechoic areas < 2 mm, Grade 3 multiple hypoechoic areas 2 to 6 mm, and Grade 4 multiple hypoechoic areas > 6 mm. For each participant at each timepoint, 4 grades will be obtained, one for each parotid and submandibular gland. The SGUS score is the numeric sum of the 4 individual grades.

7.1.2. EULAR Sjögren's Syndrome Disease Activity Index

The ESSDAI assesses 12 domains: constitutional, lymphadenopathy/lymphoma, glandular, articular, cutaneous, pulmonary, renal, muscular, peripheral neuropathy, central nervous system, hematologic, and biologic.

7.1.3. Salivary Flow

Stimulated and unstimulated salivary flow will be measured at visits.

7.1.4. Patient-Reported Outcomes

Patient-reported outcome instruments will be given to participants for completion at study visits.

7.1.4.1. Dryness Questionnaire

The dryness questionnaire will ask participants to rate the dryness of eyes, mouth, or vagina (female participants only) with 24-hour recall using an 11-point numerical rating system ranging from 0 (no dryness) to 10 (worst imaginable).

7.1.4.2. EULAR Sjögren's Syndrome Patient Reported Index

The ESSPRI consists of 3 items, each with a 0 (no symptom) to 10 (maximum imaginable symptom) scale. The 3 items are dryness, fatigue, and pain. The recall period is 2 weeks.

7.1.4.3. Patient Global Impression of Change Questionnaire

The PGIC asks a single question regarding how the patient is feeling since beginning new therapy. The questionnaire uses a 7-point scale ranging from "very much worse" to "very much improved," with the midpoint as no change.

7.1.4.4. Female Sexual Function Index

The FSFI is a brief, self-report measure of female sexual function (female participants only). The questionnaire contains 19 items covering 6 domains of sexual function. The recall period is 4 weeks.

7.1.4.5. PROMIS Fatigue Short Form

The PROMIS fatigue short form includes 7 items with a rating scale of 1 to 5. The recall period is 7 days.

7.1.4.6. European Quality of Life 5 Dimensions Questionnaire

The EQ-5D is a standardized measure of health status. It consists of 5 questions, each with a 5-item rating scale plus a visual analog scale rating from 1 to 100 for overall health status. The questionnaire probes the participants' responses for the current day.

7.2. Analysis of Efficacy Endpoints

The efficacy endpoints include the following:

- Proportion of participants with a 1 point or greater improvement on the SGUS score for parotid and submandibular glands at Week 4 and Week 12.
- Change and percentage change in SGUS score from baseline at Week 4 and Week 12.
- Change and percentage change in stimulated and unstimulated whole salivary flow from baseline at Weeks 4, 8, and 12.
- Change and percentage change in ESSDAI at Week 12.
- Change and percentage change in ESSPRI at Weeks 4, 8, and 12.
- Change and percentage change in symptom scores for dryness of eyes, mouth, and vagina and in total symptom scores in female at Weeks 4, 8, and 12.
- Proportions of participants in each PGIC category at Weeks 4, 8, and 12.
- Change and percentage change in PROMIS Fatigue short form at Weeks 4, 8, and 12.
- Change and percentage change in FSFI at Weeks 4, 8, and 12 (female participants only).
- Change and percentage change in EQ-5D at Weeks 4, 8, and 12.

Category variables will be summarized using descriptive statistics including sample size, frequency, and percentages. Continuous variables will be summarized using descriptive statistics including sample size, mean, median, standard deviation, minimum, and maximum. For endpoints with clinically meaningful subscores, these subscores will also be summarized.

[REDACTED]

8. SAFETY AND TOLERABILITY

[Appendix A](#) provides a list of planned tables and listings. Sample data displays are included in a separate document.

8.1. General Considerations

Summary tables may be replaced with listings when appropriate. For instance, an AE frequency table may be replaced with a listing if it only contains a few unique PTs reported on relatively few participants.

Unless otherwise stated, table summaries will be limited to AEs occurring within 30 days of the last administration of study drug.

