6.6. Concomitant Medications and Procedures

All concomitant medications and treatments (including over-the-counter or prescription medicines, vitamins, vaccines, and/or herbal supplements) must be recorded in the eCRF. Any prior medication received up to 28 days before the first dose of study treatment and 30 days after the last dose of study treatment will be recorded in the eCRF. A detailed history of prior

medications use related to SS in the year before screening will be also be collected, as well as response to each treatment and reason for discontinuation.

Any addition, deletion, or change in the dose of these medications will also be recorded. Concomitant medications administered after 30 days after the last dose of study treatment should be recorded for SAEs as defined in Section 9.3. Concomitant treatments/procedures that are required to manage a participant's medical condition during the study will also be recorded in the eCRF. The medical monitor should be contacted if there are any questions regarding concomitant or prior therapy.

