9.4. Reporting of Serious Adverse Events

All SAEs, regardless of suspected causality (eg, relationship to study drug, or study procedure[s]), occurring after the participant has signed the ICF through the last study visit or 30 + 7 days after the last dose of study drug, whichever occurs later, must be reported to the sponsor (or designee) within **24 hours** of learning of its occurrence, unless otherwise specified by the Protocol. The investigator will submit any updated SAE data to the sponsor (or designee) within 24 hours of it being available.

Investigators are not obligated to actively seek AE or SAE information after conclusion of the study participation. However, if the investigator learns of any SAE, including a death, at any time after a participant has been discharged from the study, and he/she considers the event to be reasonably related to the study treatment or study participation, the investigator must notify the sponsor (or designee) within 24 hours of becoming aware of the event.

After the initial AE/SAE report, the investigator is required to proactively follow each participant at subsequent visits/contacts. All SAEs will be followed until resolution, stabilization, the event is otherwise explained, or the participant is lost to follow-up (as defined in Section 7.3).

Prompt notification by the investigator to the sponsor of a SAE is essential so that legal obligations and ethical responsibilities towards the safety of participants and the safety of a study treatment under clinical investigation are met.

If the SAE is not documented in the **IB** for the study drug (new occurrence) and is thought to be related to the sponsor's study drug, the sponsor or its designee may urgently require further information from the investigator for reporting to health authorities. The sponsor or its designee may need to issue an Investigator Notification to inform all investigators involved in any study with the same drug that this SAE has been reported. Suspected Unexpected Serious Adverse Reactions will be collected and reported to the competent authorities and relevant ethics committees in accordance with Directive 2001/20/EC, or as per national regulatory requirements in participating countries.

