8.2. Adverse Events

8.2.1. Adverse Event Definitions

A TEAE is any AE either reported for the first time or worsening of a pre-existing event after first administration of study drug. Analysis of AEs (as discussed below) will be limited to TEAEs, but data listings will include all AEs regardless of their timing in relation to study drug administration.

Adverse events will be tabulated by MedDRA PT and SOC. Severity of AEs will be graded using the NCI CTCAE. The CTCAE v4.03 (2010) is used for this study. The CTCAE reporting guidelines and grading details are available on the Cancer Therapy Evaluation Program website.

The subset of AEs considered by the investigator to be related to study drug will be considered to be treatment-related AEs. The incidence of AEs and treatment-related AEs will be tabulated. Serious AEs (SAEs) will also be tabulated.

Any missing onset date, causality, or severity must be queried for resolution. Unresolved missing causality and severity will be handled according to the following rules:

- An unresolved missing causality will be considered treatment-related.
- An unresolved missing severity will be identified as an unknown severity.

For purposes of analysis, all AEs will be considered TEAEs unless the AE can unequivocally be defined as not treatment-emergent.

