8.2.2. Adverse Event Summaries

An overall summary of AEs will include the following:

- Number (%) of participants reporting any TEAEs
- Number (%) of participants reporting any SAEs
- Number (%) of participants reporting any Grade 3 or 4 TEAEs
- Number (%) of participants reporting any treatment-related TEAEs
- Number (%) of participants who temporarily interrupted study treatment because of TEAEs
- Number (%) of participants who permanently discontinued study treatment because of TEAEs
- Number (%) of participants who had a TEAE leading to death

The following summaries will be produced by MedDRA term (if 2 or fewer participants appear in a table, a listing may be appropriate):

- Summary of TEAEs by SOC and PT
- Summary of TEAEs by PT in decreasing order of frequency
- Summary of TEAEs by SOC, PT, and maximum severity
- Summary of treatment-related AEs by SOC and PT
- Summary of treatment-related AEs by PT in decreasing order of frequency
- Summary of treatment-related AEs by SOC, PT, and maximum severity
- Summary of Grade 3 or 4 AEs by SOC and PT
- Summary of Grade 3 or 4 treatment-related AEs by SOC and PT
- Summary of TEAEs leading to death by SOC and PT
- Summary of treatment-emergent SAEs by SOC and PT
- Summary of treatment-emergent SAEs by PT in descending order of frequency
- Summary of treatment-related SAEs by SOC and PT
- Summary of TEAEs leading to dose interruption by SOC and PT
- Summary of TEAEs leading to discontinuation of treatment by SOC and PT
- Summary of nonserious TEAEs by SOC and PT

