3.2 Adverse Events		
3.2.1	Overall Summary of Treatment-Emergent Adverse Events	FAS
3.2.2	Summary of Treatment-Emergent Adverse Events by MedDRA System Organ Class and Preferred Term	FAS
3.2.3	Summary of Treatment-Emergent Adverse Events by MedDRA Preferred Term in Decreasing Order of Frequency	FAS
3.2.4	Summary of Treatment-Emergent Adverse Events by MedDRA System Organ Class, Preferred Term, and Maximum Severity	FAS
3.2.5	Summary of Grade 3 or Higher Treatment-Emergent Adverse Events by MedDRA System Organ Class and Preferred Term	FAS
3.2.6	Summary of Treatment-Related Adverse Events by MedDRA System Organ Class and Preferred Term	FAS
3.2.7	Summary of Treatment-Related Adverse Events by MedDRA Preferred Term in Decreasing Order of Frequency	FAS
3.2.8	Summary of Treatment-Related Adverse Events by MedDRA System Organ Class, Preferred Term, and Maximum Severity	FAS
3.2.9	Summary of Grade 3 or Higher Treatment-Related Treatment-Emergent Adverse Events by MedDRA Preferred Term	FAS
3.2.10	Summary of Treatment-Emergent Adverse Events Leading to Death by MedDRA System Organ Class and Preferred Term	FAS
3.2.11	Summary of Treatment-Emergent Serious Adverse Events by MedDRA System Organ Class and Preferred Term	FAS
3.2.12	Summary of Treatment-Emergent Serious Adverse Events by MedDRA Preferred Term in Decreasing Order of Frequency	FAS
3.2.13	Summary of Treatment-Related Serious Adverse Events by MedDRA System Organ Class and Preferred Term	FAS
3.2.14	Summary of Treatment-Emergent Adverse Events Leading to Dose Interruption by MedDRA System Organ Class and Preferred Term	FAS
3.2.15	Summary of Treatment-Emergent Adverse Events Leading to Discontinuation of Treatment by MedDRA System Organ Class and Preferred Term	FAS
3.2.16	Summary of Nonserious Treatment-Emergent Adverse Events by MedDRA System Organ Class and Preferred Term ^a	FAS

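### SAP 8.1 cuts AE tables at 30 days after last dose, so a later-onset SAE or fatal AE that Protocol 9.4 makes reportable would be listed but not counted

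*SAP*

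**What the plan says.** **Table window.** SAP 8.1 sets a default for the safety section: "table summaries will be limited to AEs occurring within 30 days of the last administration of study drug". The rule yields to any different statement elsewhere. SAP 8.2.1, SAP 8.2.2 and the Appendix A table list give none. The table shells and the Standard Safety Tables conventions that Appendix A refers to are separate documents, not available here.

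**Reporting window.** Protocol 9.4 has every SAE, related or not, reported from consent "through the last study visit or 30 + 7 days after the last dose of study drug, whichever occurs later". Protocol 8.7 carries AE and SAE reporting to the longest of at least 30 days after last dose, the follow-up visit, or resolution. Protocol 8.3.1 has AEs monitored for at least 30 days after last dose.

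**What is to be counted.** Protocol 10.4.2 and SAP 8.2.1 define a TEAE by its start after first dose and give no upper limit. SAP 8.2.1 adds that "all AEs will be considered TEAEs unless the AE can unequivocally be defined as not treatment-emergent". SAP 8.2.2 includes the line "Number (%) of participants reporting any SAEs", a line for TEAEs leading to death, and by-term tables of SAEs and of TEAEs leading to death. In Appendix A the overall table is 3.2.1, "Overall Summary of Treatment-Emergent Adverse Events".

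**Listings.** SAP 8.2.1 keeps AEs of any timing in the listings. Appendix A includes Listing 2.7.3 for SAEs and Listing 2.7.5 for AEs leading to death.

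**Declared changes.** SAP 10.1 reports no departure from the protocol-defined analyses.

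**The concern.** An SAE that starts on, say, day 34 after last dose is reportable under Protocol 9.4 and is a TEAE under both documents. Only the 30-day sentence in SAP 8.1 keeps it out of the tables. The line for participants with any SAE would then not cover the period in which SAEs must be reported, and the SAP does not declare this.

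Safety and tolerability is a key secondary objective (Protocol Table 1), and the sample size is justified by the chance of seeing AEs (Protocol 10.1, SAP 3.3). Leaving such events out can only lower the tabulated SAE and death counts. With about 12 participants, one omission is visible in a percentage.

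**Working it through.** **The plan's own safety figure.** Protocol 10.1 and SAP 3.3 give more than a 90% chance of at least one AE of interest with 12 participants and a 20% rate. Check: 1 − 0.8^12 = 0.931. The figure is confirmed and is not in dispute.

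**The two windows.**
- Table cut: day 30 after last dose (SAP 8.1).
- SAE reporting: at least day 37 (Protocol 9.4).
- Difference in duty to report: at least 37 − 30 = 7 days.

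**How much of that difference is actively followed.** Protocol 4.2 treats a participant as complete after the follow-up visit. Protocol Table 3 and section 4.1 place that visit 30 to 37 days after last dose. Protocol 9.4 does not oblige investigators to seek events once participation has ended. Active ascertainment past day 30 is therefore between 30 − 30 = 0 and 37 − 30 = 7 days. It could be longer only if the visit is timed from an EOT visit held after the last dose, as Protocol 8.7 allows. That difference in anchor is a separate matter.

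**Size, as an upper illustration.** The documents give no SAE rate, so I assume a per-participant risk p of 2% to 20% over 84 + 37 = 121 days, a constant hazard, and full ascertainment to day 37. The tables cover 84 + 30 = 114 of those days.
- Cumulative hazard: H = −ln(1 − p)
- Tabulated risk: r = 1 − exp(−H × 114/121)
- Risk that a participant's SAE is missed by the tables: p − r
- Chance that at least one of 12 is missed: 1 − (1 − (p − r))^12

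| p | r | p − r | Expected missed of 12 | Chance of at least one missed |
|---|---|---|---|---|
| 2% | 1.885% | 0.115% | 0.01 | 1.4% |
| 5% | 4.718% | 0.282% | 0.03 | 3.3% |
| 10% | 9.450% | 0.550% | 0.07 | 6.4% |
| 20% | 18.961% | 1.039% | 0.12 | 11.8% |

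If follow-up visits fall nearer day 30, fewer late events are learned of and these chances shrink. One omitted participant is 1/12 = 8.3 percentage points.

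**Effect on the sample-size rationale.** If the 20% AE rate is taken to apply over 121 days (the plan does not say so), with every visit on day 37, the chance of tabulating at least one AE of interest is 1 − (1 − 0.18961)^12 = 0.920. That is still above 90%.

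**The case against.** The best defence is that a duty to report is not a promise to tabulate. Protocol 9.4 governs what sites send to the sponsor. A SAP may set a fixed analysis window, and 30 days gives every participant the same cut-off and matches the minimum monitoring period in Protocol 8.3.1. This stands for non-serious AEs, and a reader should not infer that the 30-day cut is an error for them. It is weaker for SAEs and deaths, where the TEAE definition has no end, the SAP promises a count of any SAEs, and SAP 10.1 declares no change.

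A second defence is that nothing disappears. Dedicated SAE and death listings exist, and with about 12 participants each case can be read individually. SAP 8.1 also says "Summary tables may be replaced with listings when appropriate", and for by-term tables SAP 8.2.2 adds "if 2 or fewer participants appear in a table, a listing may be appropriate". This mitigates the problem but does not remove it. The replacement is optional, its two-participant threshold is attached to the by-term tables rather than the overall summary, and the reported percentages come from the tables.

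Three stronger readings are tempting and not supported:
- **That at least 7 days of follow-up, or 12 × 7 = 84 participant-days, are lost for certain.** Those figures describe the duty to report. Active ascertainment may be zero days past day 30, and withdrawal of consent ends collection altogether.
- **That the protocol expects late-onset SAEs.** Protocol 6.6 says "Concomitant medications administered after 30 days after the last dose of study treatment should be recorded for SAEs", but this fits equally well with treatment of an SAE that began by day 30 and is continuing.
- **That late SAEs are definitely not tabulated.** The SAP rule allows exceptions, and the shells and standard conventions could contain one.

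**Conclusion.** The mismatch is real but minor. As the SAP stands, and if the documents not available here set no other window, a reported SAE or fatal AE with onset after day 30 would be in Listings 2.7.3 and 2.7.5 but absent from the SAE and death tables and from those lines of Table 3.2.1. This takes the SAP's word for an event falling in the window to mean onset, which is the natural reading but is not stated. On that reading, a death after day 30 from an AE that began earlier is still counted.

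The chance that any participant is left out is at most about 1.4% to 11.8% under the assumptions above, all of which are mine rather than the plan's. The sample-size rationale is unaffected, and all analyses are exploratory (SAP 3.2).

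**What to change.** In SAP 8.1:
1. State that the cut applies to AE onset date.
2. Run the SAE and death tables, and the SAE and death lines of the overall summary, through the reporting window in Protocol 9.4.
3. Keep the 30-day cut for the other AE tables, with a footnote giving the number of later-onset AEs that are listed only.
4. Note the window in SAP 10.1.

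If the sponsor prefers 30 days for SAEs as well, it should say so in SAP 10.1 and footnote the excluded events.

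The cost is a few SAP sentences and a footnote, with no new data. The disadvantages are slightly unequal windows between participants and between SAE and other AE rows, and the entry of a few late events that are less likely to be drug-related.
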